### **8.1.4 Efficacy Analysis**

All efficacy analyses will be carried out using the FAS population, which includes all randomized subjects who receive at least one dose of study drug.

#### **8.1.4.1 Efficacy Analysis for Period 1**

For all efficacy analysis in Period 1, the three placebo groups (Groups 4, 5 and 6) will be combined and treated as one placebo group for analysis purposes.

##### **8.1.4.1.1 Primary Efficacy Variables**

The primary endpoint in Period 1 (at Week 12) is the proportion of subjects achieving ACR20 response at Week 12. Analysis of the primary endpoint will be conducted on the FAS based on treatment as randomized.

The dose-response relationship among the upadacitinib groups and the combined placebo group will be characterized for ACR20 at Week 12. The dose-response curve will be shown graphically with confidence intervals (CIs) for each dose and a non-flat dose

response relationship will be demonstrated using Cochran-Armitage test. The statistical test will be at two-sided significance level of 0.05.

Nominal comparison of the primary endpoint will be made between each upadacitinib group and the combined placebo group using the Cochran-Mantel-Haenszel test adjusting for main stratification factors. For the primary analysis, Non-Responder Imputation (NRI) will be used. The analysis will be repeated using Observed Cases (OC). Supportive analysis will also be conducted on the Per Protocol Analysis Set.

The primary efficacy analyses will also be performed in demographic subgroups including age, gender, weight and body mass index (BMI) to assess the consistency of the treatment effect. Additional subgroup analyses based on baseline disease characteristics and stratification factors will also be conducted.

#### **8.1.4.1.2 Key Secondary Efficacy Variables**

Key secondary endpoints (at Week 12) are listed in Section [5.3.3.1.2](#):

For binary endpoints, frequencies and percentages will be reported for each treatment group. Similar analyses as for the primary endpoint will be conducted.

For continuous endpoints, the mean, standard deviation, median, and range will be reported for each treatment group. Pairwise comparisons for each of the upadacitinib treatment groups and the combined placebo group will be carried out using the analysis of covariance model with treatment group as the fixed factor, and the corresponding baseline value and the main stratification factors as the covariates.

See Section [8.1.4.1.5](#) for imputation methods.

#### **8.1.4.1.3 Other Efficacy Variables**

Additional secondary efficacy variables are listed in Section [5.3.3.1.3](#) and will be summarized for all visits. For binary endpoints, frequencies and percentages will be

reported for each treatment group. For continuous endpoints, the change from baseline mean, standard deviation, median, and range will be reported for each treatment group.

#### **8.1.4.1.4      Multiplicity Control for the Primary and Key Secondary Endpoints**

Multiplicity on the primary endpoint is controlled via using the Cochran-Armitage test across the multiple doses. Nominal pairwise comparison of each upadacitinib dose to placebo is also performed as supportive information.

#### **8.1.4.1.5      Imputation Methods**

The following methods will be used for missing data imputation:

**Observed Cases (OC):** The OC analysis will not impute values for missing evaluations, and thus a subject who does not have an evaluation on a scheduled visit will be excluded from the OC analysis for that visit.

**Multiple Imputation (MI):** The MI analysis imputes missing data multiple times under appropriate random variation and thus generates multiple imputed "pseudo-complete" datasets. Results will be aggregated across the multiple imputed datasets, overcoming drawbacks of the single imputation methods.

**Non-Responder Imputation (NRI):** NRI applies to binary endpoints only. In NRI analysis, subjects who prematurely discontinue the study drug will be considered non-responders after discontinuation.

The NRI approach will serve as the primary analysis approach for key binary endpoints. The MI approach will serve as the primary analysis approach for key continuous endpoints. Sensitivity analysis based on OC will also be conducted for key endpoints.

### **8.1.4.2            Long-Term Efficacy Analysis for Period 1 and Period 2 Combined**

The efficacy endpoints of long-term efficacy analysis are listed in Section [5.3.3.1.3](#) and will be summarized for all visits.

Long-term efficacy by time point will be summarized using descriptive statistics. For binary endpoints, frequencies and percentages will be summarized. For continuous endpoints, the mean and standard deviation will be reported.

### **8.1.5            Safety Analyses**

#### **8.1.5.1            General Considerations**

Safety analyses will be carried out using the Safety Analysis Set. Analyses will be conducted for Period 1 alone, as well as for Period 1 and Period 2 combined. Safety analyses are based on treatments actually received. Safety will be assessed by AEs, physical examination, laboratory assessments, ECG, and vital signs. Frequency tables and lists of subjects with treatment-emergent AEs by preferred term as in the Medical Dictionary for Regulatory Activities (MedDRA) dictionary, by system organ class, by severity, and by relationship to the study drug as assessed by the Investigator will be provided. The changes from baseline in vital signs, physical examination results, and clinical laboratory values will be analyzed in a descriptive manner. Shift of laboratory values from baseline to defined time points will be tabulated.

Missing safety data will not be imputed.

#### **8.1.5.2            Analysis of Adverse Events**

Unless otherwise specified, the following conventions apply for both the Period 1 safety analysis and the combined safety analysis of Period 1 and Period 2.

### **8.1.5.2.1 Treatment-Emergent Adverse Events (TEAE)**

AEs will be coded using MedDRA. A TEAE is defined as AE that began or worsened in severity after initiation of study drug.

AEs starting more than 30 days following the last dose of study drug will not be included in summaries of TEAEs. For subjects who continued into Period 2, the AEs that are reported in Period 2 will be captured in the combined safety analysis of Period 1 and Period 2.

As a general safety summary, the number and percentage of subjects experiencing TEAEs will be summarized for each treatment group for the following AE categories:

- All AEs;
- All severe AEs;
- All reasonably possibly related AEs;
- All SAEs;
- Frequent AEs (reported in 5% of subjects or more in any treatment group);
- Frequent reasonably possibly related AEs (reported in 5% of subjects or more in any treatment group);
- Discontinuations due to AEs;
- Death.

Additional AEs may be considered for tabulation/summary based on recommendations from Clinical and Safety as deemed appropriate.

TEAEs will be summarized and presented by system organ classes (SOCs) and preferred terms (PTs) using MedDRA. The SOCs will be presented in alphabetical order, and the PTs will be presented in alphabetical order within each SOC.

TEAE will also be summarized by maximum severity and by maximum relationship.

The AEs of special interest (including but not limited to serious infection, opportunistic infection, malignancy, non-melanoma skin cancer (NMSC), malignancy other than NMSC, lymphoma, hepatic disorder, gastrointestinal perforation, anemia, neutropenia, lymphopenia, herpes zoster, increased CPK, renal dysfunction, tuberculosis, adjudicated cardiovascular events and embolic and thrombotic events (non-cardiac, non-CNS) will be summarized. Event rate (per 100 patient years) for AEs of special interest will also be summarized for the combined safety analysis of Period 1 and Period 2.

All AEs leading to discontinuation of study drug will be presented in listing format. A listing by treatment group of TEAEs grouped by SOC and MedDRA preferred term with subject identification numbers will be generated.

#### **8.1.5.2.2      Serious Adverse Events and Death**

All treatment-emergent SAEs and AEs leading to death will also be presented in listing format. In addition, SAEs will be summarized by SOC and MedDRA PT.

#### **8.1.5.3      Analysis of Laboratory, Vital Sign, and ECG Data**

Changes from baseline by visit, and changes from baseline to minimum value, maximum value, and final values in continuous laboratory data, and vital signs will be summarized by treatment group.

Baseline values are defined as the last non-missing measurements recorded on or before the date of the first dose of study drug in Period 1.

The laboratory data will be categorized as Grade 1, Grade 2, Grade 3 and Grade 4 according to OMERACT criteria (Rheumatology Common Toxicity Criteria V.2.0). For creatine phosphokinase and serum creatinine, NCI CTC criteria will be used. The shift tables will tabulate the number and percentage of subjects with baseline and post-baseline values by grade level.

Listings will be provided for potentially clinically significant laboratory values and vital signs.

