## 8.2 Determination of Sample Size

Sample size was estimated based on the previous global Phase 2 trial (Study M13-537). Assuming an ACR20 response rate of 46% for placebo group, 62% for low dose group (7.5 mg QD), 68% for middle dose group (15 mg QD) and 80% for high dose group (30 mg QD) of upadacitinib, the sample size to have 90% power and two-sided alpha of 5% to detect a statistically significant dose-response using Cochran-Armitage test will be 42 subjects per group. And the sample size to demonstrate the superiority of upadacitinib compared to placebo will be 46 subjects to provide the 90% power and 5% of two-sided alpha. Taking 5% of drop-out rate into consideration, sample size will be 48 per group (total sample size: 192 subjects).

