## 8.3 Randomization Methods

Subjects will be randomly assigned in a 3:3:3:1:1:1 ratio to one of the six treatment groups:

- Group 1: upadacitinib 7.5 mg QD (N = 48) (Period 1) → upadacitinib 7.5 mg QD (Period 2)
- Group 2: upadacitinib 15 mg QD (N = 48) (Period 1) → upadacitinib 15 mg QD (Period 2)
- Group 3: upadacitinib 30 mg QD (N = 48) (Period 1) → upadacitinib 30 mg QD (Period 2)
- Group 4: Placebo (N = 16) (Period 1) → upadacitinib 7.5 mg QD (Period 2)
- Group 5: Placebo (N = 16) (Period 1) → upadacitinib 15 mg QD (Period 2)
- Group 6: Placebo (N = 16) (Period 1) → upadacitinib 30 mg QD (Period 2)

Randomization will be stratified by prior exposure to bDMARD (yes/no).

See Section [5.5.3](#) for details.

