Dispense study drug and subject dosing diary		X			X	X	X ^z		
Review and retain a copy of subject dosing diary and perform drug reconciliation					X	X	X		

BL = Baseline Visit; CBC = complete blood count; CCP = cyclic citrullinated peptide; D = Day; ECG = electrocardiogram; EQ-5D-5L = EuroQoL-5D; ESR = erythrocyte sedimentation rate; F/U = Follow-up; GFR = Estimated glomerular filtration rate; HAQ-DI = Health Assessment Questionnaire – Disability Index; HBV = hepatitis B virus; HCV = hepatitis C virus; HIV = human immunodeficiency virus; hsCRP = high-sensitivity C-reactive protein; MDRD = Modification of Diet in Renal Disease; PD = Premature Discontinuation; PgGA = Physicians Global Disease Activity; PK = pharmacokinetics; PPD = purified protein derivative; PtGA = Patient's Global Assessment of Disease Activity; SAE = serious adverse event; SJC = Swollen Joint Count; SF-36 = 36-Item Short Form Health Survey; TB = tuberculosis; TJC = Tender Joint Count; VAS = visual analog scale; VZV = varicella-zoster virus; Wk = Week

- If a subject prematurely discontinues study drug treatment and study participation, the procedures outlined for the Premature Discontinuation visit (PD visit) should be completed as soon as possible, preferably within 2 weeks of study drug discontinuation.
- The Baseline visit procedures will serve as the reference for all subsequent visits with the exception of the ECG which will be obtained at Screening only and used as the baseline reference.
 - This visit is 30 days after last dose of study drug for those subjects who complete Period 1 and do NOT enter Period 2. A 30-day follow-up phone call may be allowed for subjects who have completed PD visit to determine the status of any ongoing AEs/SAEs or the occurrence of any new AEs/SAEs.
 - Obtain prior to performing any study related procedures.
 - Note herpes zoster and hepatitis B vaccination status in medical history.
 - Collect serious adverse events and protocol-related non-SAE that occur after a subject signs the informed consent, prior to the first dose of study drug.
 - Prior to other procedures. For morning stiffness, duration will be captured only if NRS rating is > 0.
 - Study Procedures TB Testing for specific requirements for TB testing and TB Prophylaxis. The Latent TB risk factor assessment and TB Testing will be performed in case of Premature Discontinuation visit but not at Week 12.

Table 1. Study Activities (Period 1) (Continued)

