10.3.3.2 Assessment of Potentially Clinical Significant Laboratory Values

Long term laboratory data will be summarized based on the number and percentage of subjects meeting the criteria for potentially clinical significant laboratory values and by the actual treatment received at the time of the event occurrence. The treatment groups are the same as the ones for long term AE analysis as described in Section 10.2.2. A subject can be counted under different treatment groups if he/she switched treatment and experienced potentially clinical significant laboratory values under different treatment groups.

A listing of all subjects with any laboratory determination meeting OMERACT criteria of Grade 3 or 4 will be provided by Grade. For creatine phosphokinase, creatinine, NCI CTC criteria will be used. For each of these subjects, the whole course of the respective parameter will be listed.

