10.4 Analysis of Vital Signs

10.4.1 Variables and Criteria Defining Abnormality

Vital sign variables include sitting systolic blood pressure, sitting diastolic blood pressure, pulse rate, respiratory rate, body temperature, and weight. The criteria for potentially clinically significant vital sign findings are presented in [Table 15](#).

Table 15. Criteria for Potentially Clinically Significant Vital Sign Findings

Vital Sign	Category	Criteria for Potential Clinically Significant Vital Signs
Systolic blood pressure	Low	Value \leq 90 mmHg and decrease \geq 20 mmHg from Baseline
	High	Value \geq 160 mmHg and increase \geq 20 mmHg from Baseline
Diastolic blood pressure	Low	Value \leq 50 mmHg and decrease \geq 15 mmHg from Baseline
	High	Value \geq 105 mmHg and increase \geq 15 mmHg from Baseline
Pulse	Low	Value \leq 50 bpm and decrease \geq 15 bpm from Baseline
	High	Value \geq 120 bpm and increase \geq 15 bpm from Baseline
Respiratory Rate	Low	< 10 rpm
	High	> 24 rpm
Body temperature	High	> 39.0 degrees C (102.3 degrees F)
Weight	High	> 7% increase from baseline
	Low	> 7% decrease from baseline

10.4.2 Analysis of Vital Sign for Period 1

Analyses of mean change from baseline in continuous vital sign variables which are measured longitudinally will be performed by visits and by the "as treated" treatment groups of Upadacitinib 7.5 mg QD, Upadacitinib 15 mg QD, Upadacitinib 30 mg QD, and combined placebo groups. For each change from baseline analysis, the following summary statistics will be presented for each treatment group: sample size, baseline mean, visit mean, and the mean, standard deviation, and median of the changes from baseline. An ANOVA model with treatment as factor will be used to test statistical significance for the change from baseline mean among different treatment groups.

The number and percentage of subjects meeting the criteria for potentially clinically significant vital sign values will be summarized by "as treated" treatment group and overall.

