111. Vertigo (dizziness)	Subjective symptoms, transient, intermittent, no treatment	Objective findings, recurrent, meds relieve, occasionally interfering with function	Persistent, prolonged, interfering with daily function; partial response to medication
J. Pulmonary			
J1. Asthma	Occasional wheeze, no interference with activities	Wheezing, requires oral meds, occasional interference with function	Debilitating, requires nasal O ₂
J2. Cough	Transient, intermittent, occasional OTC meds relieve	Persistent, requires narcotic or other prescription meds for relief	Recurrent, persistent coughing spasms without consistent relief by meds, interferes with function
J3. Dyspnea	Subjective, transient, no interference with function	Symptomatic, intermittent or recurring, interferes with exertional activities	Symptomatic during daily routine activities, interferes with function, treatment with intermittent nasal O ₂ relieves
J4. Pleuritic pain (pleurisy)	Transient, intermittent symptoms, no treatment or OTC meds relieve	Persistent symptoms, requires prescription meds for relief	Prolonged symptoms, interferes with function, requires frequent narcotic pain relief
J5. Pneumonitis (pulmonary infiltrates)	Asymptomatic radiographic changes, transient, no treatment required	Symptomatic, persistent, requiring corticosteroids	Symptomatic, requiring treatment including O ₂
J6. Pulmonary function decreased (FVC or carbon monoxide diffusion capacity – DLCO)	76% – 90% of pre-treatment value	51% – 75% of pre-treatment value	26% – 50% of pre-treatment value $\leq 25\%$ of pre-treatment value

Laboratory Data			
K. Haematology			
K1. Hgb (g/dl) decrease from pre treatment	1.0 – 1.4	1.5 – 2.0	2.1 – 2.9, or Hgb < 8.0, > 7.0
K2. Leukopenia (total WBC) × 1000	3.0 – 3.9	2.0 – 2.9	1.0 – 1.9
K3. Neutropenia (× 1000)	1.5 – 1.9	1.0 – 1.4	0.5 – 0.9
K4. Lymphopenia (× 1000)	1.5 – 1.9	1.0 – 1.4	0.5 – 0.9
K5. Platelets (× 1000)	75 – LLN	50 – 74.9	20 – 49.9; platelet transfusion required
L. Chemistry			
L1. Hypercalcaemia (mg/dl)	1.1 × ULN – 11.5	11.6 – 12.5	12.6 – 13.5; or symptoms present
L2. Hyperglycemia (mg/dl) Fasting	140 – 160	161 – 250	251 – 500
L3. Hyperkalaemia (mmol/l)***	5.5 – 5.9	6.0 – 6.4	6.5 – 7.0 or any ECG change
L5. Hypocalcaemia (mg/dl)	0.9 × LLN – 7.8	7.7 – 7.0	6.9 – 6.5; or associated with symptoms
L6. Hypoglycemia (mg/dl)	55 – 64 (no symptoms)	40 – 54 (or symptoms present)	30 – 39 (symptoms impair function)
L7. Hyponatraemia (mmol/l)***	-	125 – 129	120 – 124

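### In the long-term tables by current treatment, placebo switchers on upadacitinib are judged against a pre-placebo baseline, so placebo-period change can create or hide events on the criteria that use baseline

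*Protocol*

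**What the plan says.** **Baseline.** Protocol 8.1.5.3 defines it as "the last non-missing measurements recorded on or before the date of the first dose of study drug in Period 1". SAP 4.2 (Table 1 footnotes) agrees: "The Baseline visit procedures will serve as the reference for all subsequent visits", with ECG the only exception. SAP 5.2, Table 5 ends the baseline window at Day 1. Neither document defines a new baseline when placebo subjects start upadacitinib.

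**Attribution.** SAP 10.3.3.2 tabulates long-term potentially clinically significant laboratory values "by the actual treatment received at the time of the event occurrence", and SAP 10.4.3 does the same for vital signs. The long-term treatment groups in SAP 10.2.3 combine, for each dose, subjects who started on it and subjects switched to it from placebo. A switched subject may be counted under both treatments. No rule requires a value to be new or worse since the switch.

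**Criteria that use baseline.** Laboratory significance means toxicity Grade 3 or 4. In SAP Appendix A, hemoglobin is graded as "K1. Hgb (g/dl) decrease from pre treatment", with an alternative absolute limit, and creatinine Grade 3 can be reached as a multiple of baseline or of ULN. In SAP Table 15, weight is judged purely on change, for example "> 7% increase from baseline". Systolic pressure, diastolic pressure and pulse need both a change from baseline and an absolute threshold.

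**What stays separate.** Long-term mean changes are reported by treatment sequence, so placebo switchers have their own rows (SAP 10.1, 10.3.3.1, 10.4.3).

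**The concern.** The tables credit each event to the drug being taken, but measure it from a point that, for Groups 4-6, lies 12 weeks before that drug was started. If a switcher's hemoglobin or weight moves during placebo and the value still meets the criterion at Week 16 or later, the event appears in an upadacitinib column. If the placebo-period movement is in the opposite direction, a real change on upadacitinib may not reach the threshold and goes uncounted.

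At stake is the reading of dose-specific long-term safety percentages for a small set of parameters. About a quarter of each dose column is judged against a reference that is not pre-upadacitinib. No efficacy result and no randomized safety comparison depends on it.

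**Working it through.** **1. Share of each dose column.** Protocol 8.3: "Subjects will be randomly assigned in a 3:3:3:1:1:1 ratio to one of the six treatment groups". With 192 subjects and ratio total 12, the groups are 192 × 3/12 = 48 and 192 × 1/12 = 16, which reproduces the stated sizes. Planned column per dose: 48 + 16 = 64. Switchers' share: 16/64 = 25%. Applying the plan's 5% drop-out to both parts gives 15.2/60.8 = 25%; applying it to switchers only gives 15.2/(48 + 15.2) = 24%.

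**2. Weight of one subject.** 1/64 = 1.6 percentage points. If an assumed 2%, 5%, 10% or 20% of the 16 switchers carried a placebo-period change into an upadacitinib event, the column would rise by 0.5, 1.25, 2.5 or 5.0 points (16 × rate / 64). The documents give no such rate.

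**3. Which criteria are touched.**
- Weight: change from baseline only.
- Hemoglobin: fall from pre-treatment, or an absolute limit.
- Creatinine: multiple of baseline, or multiple of ULN.
- Systolic pressure, diastolic pressure, pulse: change and absolute threshold together.
- Not touched by the choice of baseline: respiratory rate, temperature, the liver criteria in SAP 10.3.3.3, and the other graded laboratory criteria, which use absolute limits or ULN/LLN multiples.

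**4. Illustration with no drug effect.** Each subject's value follows a random walk plus visit noise. The drift SD is per 12 weeks. Visit noise is SD 0.4 g/dL for hemoglobin and 1 percentage point for weight. Any trend runs over the first 12 weeks and then stays level. Switchers are assessed at Weeks 16, 20, 24, 36 and 48; starters at Weeks 2 to 48. The events are a hemoglobin fall of at least 2.1 g/dL (the Grade 3 entry point) and a weight change above 7% either way. **All SDs and trends are assumptions.**

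| Assumption | Switchers, planned baseline | Switchers, Week 12 baseline | Difference × 16/64 | Starters, planned baseline |
|---|---|---|---|---|
| Hemoglobin, SD 0.4, no trend | 2.6% | 1.4% | +0.3 points | 2.7% |
| Hemoglobin, SD 0.4, trend -0.3 g/dL | 5.8% | 1.4% | +1.1 | 6.1% |
| Hemoglobin, SD 0.6, trend -0.3 g/dL | 14.0% | 5.3% | +2.2 | 14.6% |
| Hemoglobin, SD 0.4, trend +0.3 g/dL | 1.1% | 1.4% | -0.1 | – |
| Weight, SD 2% | 13.9% | 7.6% | +1.6 | 14.0% |
| Weight, SD 2.5% | 25.1% | 15.7% | +2.4 | – |

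Reclassification runs both ways. For hemoglobin with SD 0.4 and no trend, 2.1% of switchers are flagged only against the planned baseline and 0.9% only against Week 12. For weight with SD 2% the figures are 9.3% and 3.0%.

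**5. Reading the table.** The starters' column shows that the gap between the two baselines is not all misattribution. Week 48 lies 48 weeks from the planned baseline and 36 weeks from Week 12, and a shorter span allows less drift. Under no drug effect, switchers on the planned baseline show nearly the same rate as starters.

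**6. Is a pre-upadacitinib value available?** Yes. Protocol 5.1 starts Period 2 after the Week 12 assessments are complete. The Week 12 window for laboratory tests and vital signs in SAP Table 5 closes no later than the first Period 2 dose date.

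**The case against.** The strongest reply is that a single baseline is a deliberate convention and keeps starters and switchers on the same follow-up length. The illustration supports this: with no drug effect the planned baseline does not push the pooled percentage above the starters' own rate, and re-baselining lowers it partly because switchers then have 12 fewer weeks from reference. This stands. It rules out reading the whole Week 0 versus Week 12 gap as error.

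Three stronger readings are tempting, and the documents do not support them.
- *Laboratory and vital-sign events in general are misattributed.* Baseline enters only the criteria listed above, and a value measured on upadacitinib must still meet the criterion. A change seen only before the switch is counted under placebo. A persisting abnormality on an absolute criterion can also carry over, but that comes from the lack of a new-or-worsened rule, not from the baseline.
- *The bias runs against the drug.* An assumed upward placebo trend in hemoglobin reverses the sign.
- *Anemia rates as an event of special interest are distorted.* Those events come from a MedDRA query on reported adverse events (SAP 10.2.2.6), where laboratory baseline plays no part.

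There are also safeguards: by-sequence mean changes, a listing of the parameter's full course for every flagged subject, and no between-group test specified for the long-term tables. They let a reader trace a pre-switch onset, but they do not alter the tabulated percentages. Double counting of subjects who already met the hemoglobin criterion at Week 12 is rare in the simulation: at most 1.1% of switchers, or 16 × 0.011 = 0.18 subjects per dose.

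**Conclusion.** The mismatch is real and narrow. In the by-current-treatment tables of SAP 10.3.3.2 and 10.4.3, about a quarter of each planned dose column is assessed against a pre-placebo value on the criteria that use baseline. A placebo-period change can therefore be counted as an upadacitinib event or can mask one, at about 1.6 points per affected subject. Weight and hemoglobin are the most exposed; pressure and pulse need an absolute threshold as well, and tripled creatinine should be rare.

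The net direction and size cannot be determined from the documents. The illustrative range of about -0.1 to +2.4 points per dose group rests wholly on assumed drift, noise and trend, and includes an elapsed-time component. It should not be read as an estimate of inflation. The case for change is consistency: events attributed to upadacitinib are better referred to a pre-upadacitinib value. This is a cheap improvement and changes no primary, Period 1 or by-sequence result.

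**What to change.** In Protocol 8.1.5.3 and SAP 10.3.3.2 and 10.4.3, state that for Groups 4-6, in the tables by current treatment only, the baseline for values measured on upadacitinib is the latest available value up to the first upadacitinib dose, normally Week 12. Keep the Period 1 baseline for values measured on placebo and for the by-sequence mean-change tables. Footnote that switchers have two baselines and a shorter follow-up from their upadacitinib reference.

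While editing, correct the cross-reference in SAP 10.3.3.2, 10.3.3.3 and 10.4.3: they point to Section 10.2.2 for the long-term groups, which are defined in Section 10.2.3.

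The cost is SAP wording, one derived variable and a footnote. No new data are needed. The drawback is two references, and two lengths of follow-up, within one percentage.
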